10.6.2 Adverse Events

Analysis set: Safety

The frequency of adverse events (AEs) will be computed by counting each patient only once per MedDRA [Version 23.0 (Hierarchy)] preferred term and according to the maximum NCI CTCAE v.5.0 grade attained by the patient over the specified period. The percentage of patients with an event will be calculated using the number of patients in the safety analysis set as the denominator.

Standard Summaries of Adverse Events

Treatment Emergent Adverse Events are those that start on or after the date of first dose of study medication.

An overall summary of TEAEs (number and percentage of patients along with the number of events) will be presented with the following:

- Any non-TEAE
- Any TEAE
- Related TEAEs
- Serious TEAEs
- Related Serious TEAEs
- Grade 3 or Grade 4 TEAEs
- Related Grade 3 or Grade 4 TEAEs
- TEAEs leading to discontinuation
- Related TEAEs leading to discontinuation
- Serious TEAEs leading to discontinuation

-
- Related Serious TEAEs leading to discontinuation
 - TEAEs leading to dose interruptions
 - Fatal TEAEs
 - Related Fatal TEAEs
 - Protocol-Defined Adverse Events of Special Interest:
 - Pregnancy, abortion, birth defects/congenital anomalies
 - Overdose

Summaries showing the number of patients (n, %) along with number of events by SOC and PT will be provided for the following:

- TEAEs
- Grade 3, 4 and 5 TEAEs
- TEAE by disease subtype
- Treatment-related TEAEs
- TEAE with maximum CTCAE grade
- Treatment-Emergent SAEs
- Treatment-Related SAEs
- Treatment-related TEAEs with maximum CTCAE grade
- Deaths

The adverse events data will also be listed for individual patients.

- AEs
- Related TEAEs
- Treatment Emergent Grade 3, 4 and 5 AEs
- Treatment Related Grade 3, 4 and 5 AEs
- Treatment Emergent SAEs
- Treatment Related SAEs
- TEAE leading to discontinuation

10.6.3 Clinical Laboratory Tests

Analysis Set: Safety

Laboratory data will be presented per cycle.

The baseline measurement is the last pre-treatment measurement taken on or before Cycle1 Day1.

Absolute values and change from baseline values of Laboratory parameters will be presented using descriptive statistics (n, mean, median, standard deviation, minimum and maximum values).

The laboratory data will also be listed.

A separate listing of patients with abnormal laboratory test values will also be presented.

Based on the available data which is captured in the database, the laboratory data will be summarized for the following clinical laboratory parameters:

Hematology	Chemistry Panel I	Chemistry Panel II	Urinalysis	Other
Hematocrit	Total bilirubin	Blood glucose	Blood	PT
Hemoglobin	Alkaline phosphatase (ALP)	Urea or blood urea nitrogen	Glucose	INR
CBC with differentials	Alanine aminotransferase (ALT)	Creatinine	Protein	
Platelet count	Aspartate aminotransferase (AST)	Albumin	Specific gravity	
WBC (Total and differentials)	Lactate dehydrogenase (LDH)	Total protein	Microscopic exam	
Red blood cell count	Gamma-glutamyl transferase (GGT)	Total Cholesterol		
Absolute neutrophil count	Sodium	Triglyceride (TG)		
Absolute lymphocyte count	Potassium	LDL		
	Calcium	HDL		
	Phosphorous	TSH		
	Carbon Dioxide (CO₂) or bicarbonate	T3 (Total or Free)		
	Chloride	T4 (free)		
	Magnesium			

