#### **7.4.3 Abnormal laboratory values**

Any grade 3 or 4 laboratory abnormalities or any clinically significant grade 1 or 2 hematology or biochemistry laboratory value(s) should be recorded as an AE. Isolated laboratory abnormality without clinical significance should not be captured as AE if confirmed by the investigator. If an

abnormal laboratory value or vital sign is associated with clinical signs and/or symptoms, the sign or symptom should be reported as an AE, and the associated laboratory value or vital sign should be considered additional information that must be collected on the relevant CRF. If the laboratory abnormality is a sign of a disease or syndrome, only the diagnosis needs to be recorded on the SAE Report Form or AE CRF.

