### **9.4.2 Safety analyses**

The safety endpoints will include:

- Incidence of AEs and related AEs
- Incidence of grade 3, grade 4 AEs
- Incidence of SAEs and death
- Laboratory values
- ECG/vital signs

The safety endpoints will be listed and/or summarized. No inferential statistical analyses will be performed.

The analyses of safety will be based on the frequency of adverse events and their severity for patients in each portion who received at least one dose of study treatment. Worst toxicity grades

per patient will be tabulated for select adverse events and laboratory measurements by using NCI CTCAE criteria v5.0.

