11.	Protocol Deviations.....	19
12.	Listings.....	19
13.	References.....	20

List of Abbreviations

Abbreviation	Term
AE	Adverse Event
ATC	Anatomical Therapeutic Chemical
BID	Twice Daily
CI	Confidence Interval
CR	Complete Response
CT	Computed Tomography
CTCAE	Common Terminology Criteria for Adverse Events
DLT	Dose Limiting Toxicity
DoR	Duration of Response
DRC	Data Review Committee
ECG	Electrocardiogram
eCRF	Electronic Case Report Form
ECOG PS	Eastern Cooperative Oncology Group Performance Status
FAS	Full Analysis Set
FL	Follicular lymphoma
IgM	Immunoglobulin M
iNHL	Indolent non-Hodgkin's Lymphoma
IRB/IEC	Institutional Review Board/Independent Ethics Committee
LPL	Lymphoplasmacytic lymphoma
MedDRA	Medical Dictionary for Regulatory Activities
mITT	Modified Intent-to-Treat
MRI	Magnetic Resonance Imaging
MZL	Marginal Zone Lymphoma
NCI	National Cancer Institute
ND	Not Done
NE	Not Evaluable
NHL	Non-Hodgkin's Lymphoma
ORR	Objective Response Rate
PET	Positron Emission Tomography
PFS	Progression-Free Survival
PP	Per-Protocol
PR	Partial Response
PT	Preferred Term
Q1	First Quartile
Q3	Third Quartile
QTcF	QT interval with Fridericia's correction
SAE	Serious Adverse Events
SAP	Statistical Analysis Plan
SAS	Statistical Analysis Software
SD	Stable Disease
SOC	System Organ Class
SLL	Small Lymphocytic Lymphoma
TEAE	Treatment-Emergent Adverse Event
TID	Thrice Daily
WHO	World Health Organization
WM	Waldenstrom Macroglobulinemia

1. Amendments from Previous Version(s)

Not Applicable.

2. Introduction

Note: In this document, any text taken directly from the protocol (Number RP6530-1802, Amendment 1 to Version 1.0, Dated 15 March 2018; Amendment Version dated 04 December 2018) is *italicized*.

This SAP provides the detailed methodology for summary and statistical analyses of the data collected in study RP6530-1802. This document may modify the plans outlined in the final protocol.

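### SAP 10.6.3 omits, without explanation, the worst-CTCAE-grade-per-patient laboratory tabulation promised in Protocol 9.4.2, so no laboratory table counts the patients who reached Grade 3-4

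*SAP*

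**What the plan says.** Protocol 9.4.2 commits to worst toxicity grades that "per patient will be tabulated for select adverse events and laboratory measurements by using NCI CTCAE criteria v5.0".

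SAP 10.6.3 presents laboratory data per cycle: "Absolute values and change from baseline values of Laboratory parameters will be presented using descriptive statistics". The statistics it names are "n, mean, median, standard deviation, minimum and maximum values". It adds a full laboratory listing, and "A separate listing of patients with abnormal laboratory test values will also be presented". It mentions no CTCAE grade, no worst post-baseline value and no shift from baseline.

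In the SAP, maximum grade is tabulated only in 10.6.2, for adverse events (for example "TEAE with maximum CTCAE grade").

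Protocol 7.4.3 decides which laboratory values become adverse events. Its first sentence, on what must be entered as an event, reads "Any grade 3 or 4 laboratory abnormalities or any clinically significant grade 1 or 2 hematology or biochemistry laboratory value(s) should be recorded". Its second reads "Isolated laboratory abnormality without clinical significance should not be captured as AE if confirmed by the investigator", with no limit on grade. The section then says that a value accompanied by signs or symptoms is reported under the sign or symptom, and that a value which is a sign of a disease is recorded only under the diagnosis.

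SAP section 2 reserves the right to depart from the protocol: "This document may modify the plans outlined in the final protocol".

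**The concern.** Safety and tolerability are the secondary objective. Much of the known severe toxicity is laboratory toxicity. Protocol 1.1.2 reports related Grade 3 or higher AST/ALT elevation, neutropenia and hypophosphatemia in RP6530-1401, and hypertriglyceridemia and neutropenia in RP6530-1301. A reader of the study report will want to know how many patients reached Grade 3 or 4 on each key parameter. The protocol promised a table that answers this from the laboratory data, and the SAP does not contain it.

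The answer would then have to come from AE records, which depend on how sites read 7.4.3 and on which term they chose. If some Grade 3-4 values were not recorded as events, or were recorded under another term, the summary tables would understate severe laboratory toxicity and no laboratory table would show it.

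**Working it through.** The plan states no figure on this point, so the main check is a comparison of texts. The arithmetic illustrates size only.

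**1. Promise against plan.** Protocol 9.4.2 covers two objects: select adverse events and laboratory measurements. SAP 10.6.2 delivers the first and SAP 10.6.3 does not deliver the second. The protocol's word *select* leaves the choice of parameters to the sponsor; it does not cover choosing none. SAP section 2 permits a change, but none is declared. Protocol section 9 has the study report discuss deviations from the SAP, so an omission within the SAP could go unreported.

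**2. Whether the planned statistics can give the count.** Constructed ALT example for one cycle, n = 20, in multiples of ULN. Unaffected patients are at 0.8, one affected patient at 8.0, and any others affected at 5.5. Both affected values lie in the range above 5 to 20 x ULN that Protocol Table 4 labels Grade 3.

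| Grade 3 patients | Mean | Median | Maximum | SD |
|---|---|---|---|---|
| 1 | (19 x 0.8 + 8.0)/20 = 1.16 | 0.8 | 8.0 | 1.61 |
| 5 | (15 x 0.8 + 8.0 + 4 x 5.5)/20 = 2.10 | 0.8 | 8.0 | 2.37 |

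The maximum shows that a severe value occurred. Neither it nor the median separates one patient from five, and the mean and SD move without yielding a count. Three features of the plan add to this:

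- High maxima in several cycles may come from one patient or from several.
- Tests are run at local laboratories (Protocol 6.2.8) at about 10 sites, so a pooled absolute maximum is not itself a multiple of ULN.
- Table 4 calls for weekly or twice-weekly ALT/AST checks during transaminitis, but 10.6.3 has no rule for several values within a cycle.

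**3. Whether the AE tables can replace it.** Under 7.4.3:

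| Grade 3-4 value | Route into the AE tables |
|---|---|
| Isolated, clinically significant | Recorded as an AE |
| Isolated, judged not clinically significant | Recorded under the first sentence, not under the second |
| With signs or symptoms | Recorded under the sign or symptom |
| Sign of a disease or syndrome | Recorded under the diagnosis |

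Only the first row gives a sure count of laboratory toxicity under its own name.

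**4. How many patients might be involved.** Assumption: the RP6530-1401 rate carries over and each reported case is one patient. Related Grade 3 or higher AST/ALT elevation was 11/49 = 22.4% (exact 95% CI 11.8% to 36.6%). Out of 20 planned patients, 20 x 11/49 = 4.5 (20 x 0.118 = 2.4 to 20 x 0.366 = 7.3). For neutropenia, 3/49 = 6.1% (1.3% to 16.9%), or 1.2 of 20 (0.3 to 3.4).

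The documents do not give the share that might go unrecorded as AEs. For assumed shares f, the AE tables would show 4.5 x (1 - f) AST/ALT patients:

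| f | 0% | 10% | 25% | 50% |
|---|---|---|---|---|
| Patients shown, of 20 | 4.5 | 4.0 | 3.4 | 2.2 |

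**The case against.** **The SAP gives more than means.** A reader might infer that severe values would be hidden. They would not. The SAP plans the median, SD, minimum and maximum, a full listing and a listing of abnormal values, and with about 20 patients these can be read by eye. This stands. What is missing is the graded count per patient, which readers would have to build themselves.

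**Section 7.4.3 does not plainly exempt Grade 3-4 values.** A reader might infer that sites were free to leave them unrecorded. The first sentence requires any Grade 3 or 4 abnormality to be recorded and applies clinical significance only to Grades 1-2. The second can be read as completing that Grade 1-2 clause. This also stands: the text is ambiguous, and undercounting is not shown.

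**Other counts catch severe cases.** For related events, Table 4 ties dose actions to Grade 3 or higher transaminitis, so such a value is hard to call clinically insignificant. SAP 10.1 counts patients with dose reductions or interruptions, and 10.6.2 counts TEAEs leading to interruption. This narrows the gap, but those counts give neither the parameter nor the grade.

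**The 11/49 may not apply, and was not lost.** Those were treatment-related events reported in a T-cell lymphoma study at several dose levels, so AE tables would count similar cases. RP6530-1301, whose 35 patients included FL, MZL and WM, lists no AST/ALT elevation among its related Grade 3 or higher events. Both points stand. The figure cannot support a claim that four or five patients would go uncounted.

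**The SAP may change the plan, and the analysis is descriptive.** True, but a change should be stated and justified.

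**Conclusion.** The omission is real and undeclared: the protocol promises worst-grade tabulation of select laboratory measurements and the SAP contains none. As written, no laboratory table will show how many patients reached Grade 3 or 4. The AE tables may not fully replace it, given the conflict within 7.4.3 and the rules that move some values under a symptom or diagnosis.

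The size of any undercount is unknown and may be zero. It depends on how sites applied 7.4.3, which the documents do not show. The expected 4.5 of 20 patients with Grade 3 or higher AST/ALT elevation (2.4 to 7.3) rests on carrying over the T-cell lymphoma rate. It indicates how many patients such a table might describe, not how many would be missed.

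No hypothesis test or Part 2 decision depends on this. It affects how completely the secondary safety objective is reported, and is worth correcting because the remedy is cheap.

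**What to change.** 1. Add to SAP 10.6.3 a table of worst post-baseline CTCAE v5.0 grade per patient, set against baseline grade and including unscheduled values. The denominator should be Safety Population patients with at least one post-baseline value of that parameter. Parameters are the sponsor's choice, since the protocol says select; gradable liver, hematology and metabolic tests fit the toxicities in Protocol 1.1.2. Baseline grade is needed because inclusion criterion 7 admits platelets from 30 x 10^9/L with marrow involvement, inside the 25 to 50 x 10^9/L band that Table 3 labels Grade 3. If the table is not wanted, state and justify the departure from Protocol 9.4.2.
2. Before database lock, check every Grade 3-4 laboratory value against the AE records and report any without a matching event.
3. State in the SAP or study report which reading of 7.4.3 was applied. The SAP says the study is closed, so rewording 7.4.3 now cannot change what sites recorded. The table works under either reading.

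The cost is one standard table from data already collected and one reconciliation. Reported Grade 3-4 incidence may rise.

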**Table 3: Dose Modifications for Hematologic Toxicity**

Worst CTCAE Grade Toxicity	Action to be Taken
HEMATOLOGIC	
Neutropenia (ANC)	
Grade 3 $1.0 \times 10^9/\text{L} < \text{ANC} \leq 0.5 \times 10^9/\text{L}$	Maintain dose level. Monitor ANC at least weekly.
Grade 4 $0.5 \times 10^9/\text{L} < \text{ANC}$	First incidence: Hold* dose until resolved to $\leq$ Grade 2 or baseline, Restart Tenalisib at 400 mg BID dose level. Subsequent occurrence: Hold dose until resolved to $\leq$ Grade 2 or baseline, consider growth factor support. Discontinue if further dose modification required.

Grade 3 Febrile neutropenia ANC <1000/mm  with a single temperature of > 38.3 0C (101 0F) or a sustained temperature of ≥ 38 0C (100.4 0F) for more than one hour.	Hold* dose until resolved to ≤ Grade 2 or baseline, consider growth factor support, then reduce by 1 dose level.
Thrombocytopenia	
Grade 3 (50.0 X 10  /L < PLT ≥ 25.0 X 10  /L)	Maintain dose level. Monitor platelet count at least weekly.
Grade 4 25.0 X 10  /L < PLT	1st occurrence: Hold** dose until resolved to ≤ Grade 2 or baseline, Restart Tenalisib at 400 mg BID dose level. Subsequent Occurrences: Hold dose until to ≤ Grade 2 or baseline, consider platelet transfusion as necessary. Discontinue if further dose modification required. Note: If the count is <50 X 10  /L before initiation of therapy (e.g. in case of marrow involvement), the dose reduction should be done as per investigator's judgement.

\*If study drug is delayed >2 weeks because of an adverse event, treatment strategy should be discussed with medical monitor.

\*\* Patient receiving concomitant medication (e.g. anticoagulants, anti-platelets, aspirin, or low molecular weight heparin) must be discussed with the medical monitor for continued management.

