**Table 4: Dose Modifications for Non-Hematologic Toxicities**

NON-HEMATOLOGIC	Action to be Taken
Renal*	If serum creatinine Grade ≥3 (>3 x baseline or >3 x ULN), hold dose until ≤ grade 2. Monitor serum creatinine at least twice a week until resolution to ≤ grade 2, and then at least one week until it resolves to ≤ grade 1.
Hepatic*	
Transaminitis
 
Grade ≥ 1 Transaminitis (ALT/AST > 1-3 X ULN):
 
 
• Maintain Tenalisib dose and initiate prednisone 40 mg daily.
 
• Monitor AST/ALT weekly until resolved.
 
• Withhold Tenalisib in case of development of grade 2 transaminitis or worsening of Grade 1 transaminitis while on steroids.
 
 
Grade ≥ 3 Transaminitis (ALT/AST >5–20 X ULN):
 
 
• Withhold Tenalisib and monitor ALT/AST twice a weekly until Grade ≤1; restart Tenalisib at 400 mg BID dose level.
 
• Initiate prednisone 1 mg/kg in case no improvement with discontinuation of Tenalisib in 1 week.
 
• Monitor ALT/AST twice a weekly until Grade ≤1; restart Tenalisib at 400 mg BID dose level and taper steroid.
 
• If no immediate response to steroids within 7 days, initiate mycophenolate mofetil.
 
• In case of recurrence of transaminitis at reduced doses, discontinue Tenalisib permanently after assessing risk versus benefit.
 
 
Grade ≥ 4 Transaminitis (ALT/AST >20 X ULN):
 
 
• Tenalisib should be permanently discontinued.
 

	
Bilirubin:
 
 
• Grade <math>\geq 2</math> (<math>> 1.5-3 \times \text{ULN}</math>): Maintain Tenalisib dose. Monitor at least weekly until <math>\leq 1 \times \text{ULN}</math>
 
• Grade <math>\geq 3</math> (<math>> 3-10 \times \text{ULN}</math>): Withhold Tenalisib. Monitor at least weekly until bilirubin is <math>\leq 1 \times \text{ULN}</math>; restart Tenalisib at 400 mg BID dose level.
 
• Grade <math>\geq 4</math> (<math>> 10 \times \text{ULN}</math>): Discontinue Tenalisib permanently
 

Infection	
Grade 3 or higher sepsis or pneumonia
 
 
• Interrupt Tenalisib until infection has resolved.
 

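### SAP section 10.6.3 leaves out the table of worst laboratory grade per patient that protocol section 9.4.2 promises, and does not say it was dropped

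*SAP*

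**What the plan says.** Protocol section 9.4.2 (Safety analyses) says that worst toxicity grades "per patient will be tabulated for select adverse events and laboratory measurements by using NCI CTCAE criteria v5.0".

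SAP section 10.6.3 (Clinical Laboratory Tests) says: "Absolute values and change from baseline values of Laboratory parameters will be presented using descriptive statistics". The statistics are n, mean, median, standard deviation, minimum and maximum, by cycle. The section adds a listing of all laboratory data and a separate listing of patients with abnormal values. It does not mention CTCAE grade.

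SAP section 10.6.2 tabulates maximum CTCAE grade, but only for treatment-emergent adverse events. SAP section 12 adds no graded laboratory output.

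On departures from the protocol, the SAP introduction states only: "This document may modify the plans outlined in the final protocol".

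Protocol section 7.4.3 governs which laboratory values become adverse events. Some values must enter the adverse-event data: "Any grade 3 or 4 laboratory abnormalities or any clinically significant grade 1 or 2 hematology or biochemistry laboratory value(s) should be recorded". Others stay out of it: "Isolated laboratory abnormality without clinical significance should not be captured as AE if confirmed by the investigator".

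**The concern.** A specific protocol output has gone missing without a word. Elsewhere the SAP names what it drops and gives a reason: Part 2 and the dose-limiting-toxicity data (notes to section 5.1), and confidence intervals by subtype (section 10.5). It gives no such statement for the laboratory table. Protocol section 9 asks the study report to discuss deviations from the SAP, so an output absent from the SAP itself may never be explained.

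Safety is the only secondary objective, and laboratory toxicity matters for this drug. Protocol section 1.1.2 reports treatment-related Grade 3 or higher AST/ALT elevation with n=11 in a T-cell lymphoma study of 49 treated patients. Protocol section 3.5.5 asks for monitoring of liver enzymes and neutropenia. Tables 3 and 4 tie dose or management actions to grades of neutrophils, platelets, ALT/AST, bilirubin and creatinine; for example, "Withhold Tenalisib in case of development of grade 2 transaminitis or worsening of Grade 1 transaminitis while on steroids". A reader will want to know how many patients reached each grade, and summaries by cycle do not show that. A table built from measurements would also check whether abnormal values were recorded as adverse events as section 7.4.3 requires.

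**Working it through.** There is no figure in the plan to reproduce. The check has three parts: a comparison of texts, a constructed example, and a count of scheduled blood draws.

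**1. Protocol commitment against SAP outputs**

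| Protocol 9.4.2 commitment | Where it appears in the SAP |
|---|---|
| Worst grade per patient, adverse events | 10.6.2: maximum-grade tables for all and for related treatment-emergent events |
| Worst grade per patient, laboratory measurements | Not in 10.6.3, not in 12 |

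**2. What the adverse-event tables can and cannot supply**

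Under protocol section 7.4.3, Grade 3/4 values and clinically significant Grade 1/2 values should reach the maximum-grade tables. The same section leaves three routes by which a graded value does not appear there as a laboratory event:

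- An isolated abnormality judged not clinically significant is not captured. That sentence is not limited to Grades 1 and 2.
- If the value comes with signs or symptoms, the sign or symptom is the event and the value is supporting information.
- If the value is a sign of a disease, only the diagnosis is recorded.

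In addition, SAP 10.6.2 counts a patient once per preferred term. If ALT and AST are coded as separate terms, no row counts patients by the worse of the two.

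**3. Constructed example: what summaries by visit hide**

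Assumptions: 20 treated patients (the planned number), every baseline ALT 0.8 x ULN. At each of C2D1, C3D1 and C4D1 one patient has 4.0 x ULN and 19 have 0.8. In protocol Table 4 the value 4.0 lies between the Grade 1 range (>1-3) and the Grade 3 range (>5-20).

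At each visit:

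- Mean = (4.0 + 19 x 0.8)/20 = 19.2/20 = 0.96
- Median = 0.80, minimum = 0.8, maximum = 4.0
- SD = sqrt[((4.0 - 0.96)^2 + 19 x (0.8 - 0.96)^2)/19] = sqrt[(9.2416 + 0.4864)/19] = sqrt(0.512) = 0.716
- Change from baseline: one value of 3.2 and 19 of 0, so mean 3.2/20 = 0.16, with the same SD of 0.716

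| Scenario | Per-visit statistics | Patients ever at 4 x ULN |
|---|---|---|
| Same patient at all three visits | as above | 1/20 = 5% |
| A different patient at each visit | as above | 3/20 = 15% |

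The tables in SAP 10.6.3 are identical in the two scenarios. A worst-grade table separates them.

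**4. Scheduled post-baseline draws through C8D1 (protocol Table 1)**

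- Blood count and chemistry panel I (ALT, AST, bilirubin): C1D15, C2D1, C2D15, C3D1, C3D15, C4D1, C5D1, C6D1, C7D1, C8D1 = 10
- Chemistry panel II (creatinine): C3D1, C5D1, C8D1 = 3

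Each has an end-of-treatment draw as well. Creatinine is therefore sampled far less often unless a toxicity triggers the Table 4 rule, "Monitor serum creatinine at least twice a week until resolution to" Grade 2 or below. After cycle 8, laboratory tests are at the investigator's discretion (protocol section 6.6). A worst-grade table has to disclose these differences.

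**The case against.** The strongest reply is that the SAP governs. Protocol section 9 allows its methods to be revised and leaves presentation to the SAP, and no rule demands an itemised list of changes. The commitment itself is loose: the same section 9.4.2 allows safety endpoints to be listed or summarised, and the qualifier on which events are selected may also apply to laboratory parameters. This stands in part. Silence about the change is a lapse of good practice and breaks no stated rule. But freedom to choose parameters does not cover choosing none.

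Second, most of what matters clinically should reach the adverse-event tables. The dose rules for neutrophils, platelets and creatinine start at Grade 3, which section 7.4.3 sends there. For ALT/AST even Grade 1 calls for prednisone, so a value acted on is hard to call insignificant. In the example, ALT of 4 x ULN would ordinarily be an adverse event, and the two scenarios would then separate. This largely stands and is the main reason the point is minor. It depends, however, on complete recording by investigators, which only a measurement-based count would check.

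Third, nothing excludes unscheduled values from the listings, and with about 20 patients the counts can be rebuilt. That stands: the missing item is the tabulated count, and the data remain available.

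Fourth, baseline grade, a combined ALT/AST row and a sampling footnote go beyond section 9.4.2. That is true. They are proposed because the table would mislead without them.

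**Conclusion.** The concern holds, at minor weight. The SAP omits a protocol-specified safety table and does not declare the omission. The loss is mainly a count of patients by worst laboratory grade drawn from the measurements, including values not recorded as adverse events and peaks at unscheduled visits.

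The 5% against 15% contrast is an illustration. It assumes 20 treated patients and applies only to the extent that the values are not recorded as adverse events; the documents do not show how often that happened. No efficacy result, hypothesis test or decision about Part 2 depends on this point.

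**What to change.** Add one table to SAP section 10.6.3: number and percentage of safety-set patients by worst post-baseline CTCAE v5.0 grade, from scheduled and unscheduled values, for ALT, AST, bilirubin, creatinine, neutrophils and platelets. Each has a rule in protocol Tables 3 and 4.

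- Add a row counting each patient once for the worse of ALT and AST.
- Show baseline grade beside worst grade. Entry allows ALT/AST up to 1.5 x ULN, or 2.5 x ULN with liver involvement, and anything above 1 x ULN is already Grade 1 by Table 4. Platelets may start at 30 x 10^9/L with marrow involvement, which is Grade 3 in Table 3 (25-50). Table 3 itself recognises this: for counts below 50 "before initiation of therapy (e.g. in case of marrow involvement), the dose reduction should be done as per investigator's judgement".
- Give the number of patients with at least one post-baseline value, and state the denominator, since SAP section 10 otherwise defaults to patients with a non-missing assessment.
- Footnote the 10 against 3 scheduled draws through C8D1 (plus end of treatment) and the discretionary sampling after cycle 8.

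If the sponsor prefers not to add the table, the SAP should say that the section 9.4.2 laboratory table is dropped and why. That closes the documentation gap but does not supply the counts.

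The cost is one table. Neutrophils and platelets need no ULN. The other four need each local laboratory's ULN: protocol section 11.3 requires normal ranges on file before the trial starts, but the documents do not say whether they are in the database.
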